4.2 Statistical methods

Kaplan-Meier estimates

An estimate of the survival function will be constructed using Kaplan-Meier (product-limit) method as implemented in PROC LIFETEST with METHOD=KM option. The PROC LIFETEST statement will use the option CONFTYPE=LOGLOG.

Median survival will be obtained along with 95% confidence intervals calculated from PROC LIFETEST output using the method of [Brookmeyer and Crowley 1982]. Kaplan-Meier estimates of the survival function with 95% confidence intervals at specific time points will be summarized. The standard error of the Kaplan-Meier estimate will be calculated using Greenwood's formula [Collett 1994].

4.3 Imputation rules

4.3.1 AE, ConMeds and safety assessment date imputation

Table 4-1 Imputation of start dates (AE, Symptoms and complications, concomitant medications medical history, health resources utilization, non-drug treatment and other medical interventions)

Missing Element	Rule
day, month, and year	
 • No imputation will be done for completely missing dates
day, month	
 • If available year = year of study treatment start date (index date) then 
 ○ If stop date contains a full date and stop date is earlier than study treatment start date then set start date = 01JanYYYY ○ Else set start date = study treatment start date. • If available year > year of study treatment start date then 01JanYYYY • If available year < year of study treatment start date then 01JulYYYY
Day	
 • If available month and year = month and year of study treatment start date then 
 ○ If stop date contains a full date and stop date is earlier than study treatment start date then set start date= 01MONYYYYY. ○ Else set start date = study treatment start date. • If available month and year > month and year of study treatment start date then 01MONYYYYY • If available month and year < month year of study treatment start date then 15MONYYYYY

Table 4-2 Imputation of end dates (AE, Symptoms and complications, concomitant medications, medical history, health resources utilization, non-drug treatment and other medical interventions)

Missing Element	Rule (*= earliest between (last treatment date plus 30 days, death date, cut-off date)
day, month, and year	
 Completely missing end dates (incl. ongoing events) will be imputed by the end date of the study period*
day, month	
 If partial end date contains year only, set end date = earliest of 31DecYYYY or end date of the study period*
Day	
 If partial end date contains month and year, set end date = earliest of last day of the month or end date of the study period*

Table 4-3 Imputation of start dates for assessments (Laboratory evaluation, vital signs, ECG, growth data, medical procedure (surgery), death, questionnaires, PROS disease history)

Missing Element	Rule
day, month, and year	
 No imputation will be done for completely missing dates
day, month	
 If available year = year of study treatment start date (index date) then set start date = max(study treatment start date, 01JulYYYY). If available year > year of study treatment start date then 01JanYYYY If available year < year of study treatment start date then max (01JulYYYY , Pre-Index date)
Day	
 o If available month and year = month and year of study treatment start date then set start date = max(study treatment start date, 15MONYYYY). • If available month and year > month and year of study treatment start date then 01MONYYYY • If available month and year < month year of study treatment start date then max(15MONYYYY , Pre-index date)

If imputed date is before birth or after DCO, death date or study discontinuation the last will be used.

If imputed end date is earlier than the start date or of the imputed start date then the imputed end date = start date.

Any AEs and ConMeds with partial/missing dates will be displayed as such in the data listings.

Any AEs and ConMeds which are continuing as per data cut-off will be shown as 'ongoing' rather than the end date provided.

For treatment start and end date if day is missing then it will be set to be the 15th of the month and if both month and day are missing, is defaulted to 01-Jan.

Treatment end date = min (imputed treatment end date*, death date, cut-off date).

If Imputed treatment end date < Treatment start date then Treatment end date= treatment start date.

Similar imputation will be performed for similar assessment in the pre-index period, more details as will be provided in the PDS.

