4.1 General definitions

Study treatment

The term study treatment or study drug will be used in this document and will refer to alpelisib.

Date of first administration of study drug

The date of first administration of alpelisib is defined as the first date when a non-zero dose of alpelisib is administered and recorded in the (e)CRF. This date is referred to as index date and used as reference start date.

Date of last administration of study drug

The date of last administration of alpelisib is defined as is the last date when a nonzero dose of alpelisib is administered and recorded in the (e)CRF.

Study day

The study day, describes the day of the event or assessment date, relative to the reference start date. The study day is defined as:

- The date of the event (visit date, onset date of an event, assessment date etc.) – reference start date + 1 if event is on or after the reference start date;
- The date of the event (visit date, onset date of an event, assessment date etc.) – reference start date if event precedes the reference start date.

Time unit

A year length is defined as 365.25 days. A month length is 30.4375 days (365.25/12). If duration is reported in months, duration in days will be divided by 30.4375. If duration is reported in years, duration in days will be divided by 365.25.

Baseline

For safety and efficacy evaluations, the last available assessment on or before the date of start of alpelisib is defined as “baseline” assessment.

On-treatment assessment/event and observation periods

For adverse event reporting the overall observation period will be divided into two mutually exclusive segments:

1. *pre-index date/pre-treatment period*: from up to 24 weeks prior to the index date through to the day prior to the index date.
2. *post-index date/on-treatment period*: from date of first administration of study treatment to 30 days after date of last administration of alpelisib (including start and stop date).

Safety summaries (tables, figures) include only data from the on-treatment period with the exception of baseline data which will also be summarized where appropriate (e.g. change from baseline summaries).

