4.3.1.1 Imputations and study periods (pre-index, study period)

If "Start" and "End" dates are completely missing with no specification of whether the event is "Ongoing", then the event will be assumed to be happening during the study period.

If "Start" and "End" dates are both missing and "Ongoing" is specified, then the event is assumed to be happening during study period.

In case the "Start" date is completely missing but the "End" date is non- missing or partially missing:

- if end date is in the study period, then the therapy will be assigned only to the study period.
- if end date is before the index date, then the event will be assigned to the pre-index period only.

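### SAP Table 4-1 tests for a pre-treatment stop date only when that date is complete, so a record with a year-only start in the index year and a month-year stop before the index month is moved to Day 1

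*SAP*

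**What the plan says.** SAP section 4.3.1, Table 4-1, gives the start-date rules for several record types: "Imputation of start dates (AE, Symptoms and complications, concomitant medications medical history, health resources utilization, non-drug treatment and other medical interventions". In the row for a missing day and month, when the recorded year equals the index year, there are two branches. The first is "If stop date contains a full date and stop date is earlier than study treatment start date then set start date = 01JanYYYY". The second is "Else set start date = study treatment start date".

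Table 4-2 completes partial stop dates. For a stop with only the day missing the rule begins "If partial end date contains month and year, set end date = earliest of last day of the month", and the result is capped at the end of the study period.

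The text after Table 4-3 adds a consistency rule: "If imputed end date is earlier than the start date or of the imputed start date then the imputed end date = start date".

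Section 4.3.1.1 assigns records to periods. Where the start date is completely missing and the end date is complete or partial, "if end date is before the index date, then the event will be assigned to the pre-index period only".

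Section 4.1 defines the study day as event date minus "reference start date + 1 if event is on or after the reference start date", so the index date is Day 1.

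**The concern.** Table 4-1 is meant to keep a record in the pre-index period when its stop date shows that it ended before treatment; its first branch does this. The test is limited to complete stop dates, although a stop date with month and year can prove the same thing. When it does, the SAP overrides what the chart shows.

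The record types concerned are reported separately before and after the index date, or classified by it:

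- **Objective 5.** Under SAP 3.6 a medication starting on the index date is concomitant, so a PROS drug stopped earlier would be counted as concomitant. Non-drug treatments are summarized over the study period.
- **Objective 6.** Symptoms and complications are reported from the index date onward and, separately, for the pre-index period. A resolved symptom would change sides.
- **Objective 8.** Hospitalizations and ER visits are likewise reported separately for the two periods. An affected stay would also shrink to one day, so duration as well as count would be wrong.

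The direction is mixed. Moving symptoms or hospital stays from before to after treatment works against alpelisib. The pain-reduction indicator in SAP 3.6 could move the other way: a pain drug stopped earlier would appear on the index date and be absent at Week 24, which could look like a fall in the number of drugs.

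**Working it through.** The plan states no figure to reproduce. The check is to apply the rules literally, in the order in which they are printed.

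**1. Worked record.** Assumed dates: index 10-Jun-2019, recorded start 2019, recorded stop February 2019.

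- Table 4-1: the start year equals the index year and the stop is not a full date, so the second branch gives start = 10-Jun-2019.
- Table 4-2: the day is missing, so stop = 28-Feb-2019.
- Consistency rule: 28-Feb-2019 is before 10-Jun-2019, so stop = 10-Jun-2019.
- Study day: 10-Jun-2019 − 10-Jun-2019 + 1 = 1.

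The latest possible true stop is 28-Feb-2019. From there to the index date is 31 (March) + 30 (April) + 31 (May) + 10 (June) = 102 days. The record ended at least 102 days before treatment and is counted on study.

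**2. Neighbouring records, same index date.**

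| Recorded start | Recorded stop | Result under the SAP | Period |
|---|---|---|---|
| 2019 | 28-Feb-2019 | 01-Jan-2019 to 28-Feb-2019 | pre-index, correct |
| wholly missing | February 2019 | section 4.3.1.1 applies | pre-index, correct |
| 2019 | February 2019 | 10-Jun-2019 to 10-Jun-2019 | Day 1, wrong |
| 2018 | February 2019 | 01-Jul-2018 to 28-Feb-2019 | pre-index, correct |
| 2019 | June 2019 | 10-Jun-2019 to 30-Jun-2019 | Day 1, cannot be disproved |

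Rows 2 and 3 differ only in that the start year is known in row 3. The extra information produces the wrong period.

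**3. How far the fault extends.** Take every index date in 2019 and every month-year stop in 2019 whose last day precedes it. An index date in month m leaves m − 1 such stop months, so the number of combinations is the sum over months of (days in month) × (m − 1):

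0 + 28 + 62 + 90 + 124 + 150 + 186 + 217 + 240 + 279 + 300 + 341 = 2017 combinations.

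- Year-only start: all 2017 combinations are moved to Day 1. Keeping only index dates up to the eligibility limit of 23-Sep-2019 gives 857 (January to August) + 23 × 8 = 1041, again all moved.
- Known start month before the index month: 0 of 8751 combinations are moved, because the start becomes the 15th of that month.
- Known start month equal to the index month (the missing-day row): a possible stop month is the index month or later, so its last day is never before the index date. No case arises.
- January index date: m − 1 = 0, so no case arises.

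**4. After the change.** Testing the latest compatible stop date makes the worked record 01-Jan-2019 to 28-Feb-2019. Misassigned combinations fall from 2017 to 0. Records whose stop could fall on or after the index date still default to Day 1.

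These counts are combinations of dates, not patients or records, and show only that the fault is systematic within the pattern.

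**The case against.** **Order of imputation.** The SAP does not say whether Table 4-2 runs before Table 4-1. If stop dates were completed first and then counted as full, February 2019 would become 28-Feb-2019, the first branch would apply and the fault would vanish. This reading is possible but weak. Table 4-2 fills even completely missing stop dates, so every stop date would already be full and the full-date condition would have no purpose. The silence on order does stand as a gap.

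**Programming specification.** The SAP leaves further detail on similar imputation in the pre-index period to the PDS, which is not among the documents. It may help, but nothing in that sentence says that it overrides Table 4-1.

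**Safeguards.** Listings show partial dates for AEs and concomitant medications as recorded, and the protocol provides chronology checks and site queries. These may reveal or complete some dates, but they do not correct the summary tables where the pattern remains.

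**Scope and size.** This objection stands. A reader might infer that partially dated pre-treatment records in general are moved on study, or that objectives 5, 6 and 8 are materially distorted. The documents support neither: the pattern is specific, and its frequency is not given. A simulation in which every record already has a year-only start and a month-year stop within the 24 pre-index weeks, with index dates uniform from 2017 to 23-Sep-2019, shows how little can be said. Of the records provably finished before the index month, 71% are moved if events last 3 to 14 days. The share is 59%, 45% or 25% if durations are uniform up to 90, 180 or 365 days. These are shares of an unknown and possibly very small number of records.

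**Conclusion.** The point holds in a narrow form. Read literally, the rules misplace any record with a year-only start in the index year and a month-year stop in a month before the index month, and they conflict with section 4.3.1.1 on the same facts. The conclusion assumes that Table 4-1 is applied to the recorded stop date, which its wording favours but the SAP does not state.

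The fault cannot arise with a complete stop date, a known start month, a start year before the index year, or a January index date. The missing-day row of Table 4-1 does not produce it. Surgeries fall under Table 4-3, and lesion assessments have their own date rule in section 4.3.1.2, so the primary endpoint is unaffected. What remains exposed is a set of descriptive secondary summaries, with no hypothesis test. The size of the effect on them cannot be computed, and no single direction of bias follows. The correction is worth making because the rule contradicts the chart and costs little to repair.

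**What to change.** In the row of Table 4-1 for a missing day and month, and only there, replace the full-date condition with: the latest date compatible with the recorded stop date, full or partial, is earlier than the study treatment start date. For a month-year stop that is the last day of the month; for a year-only stop, 31 December. Apply the test before the rule that sets the imputed end date to the start date, and state the order in which start and end dates are imputed. Extending the pre-index rule of section 4.3.1.1 to year-only start dates is equivalent. Records whose stop could fall on or after the index date keep the current default.

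The cost is one condition and one sentence in the SAP, and the matching lines in the date-imputation program and the PDS. Listing the records with this date pattern would show whether any summary changes.

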## **6 Research methods**

### **6.1 Study design**

This study will be a site-based retrospective non-interventional medical chart review of pediatric and adult male and female patients with PROS. This study will abstract longitudinal information that has been previously recorded in the medical charts of patients with PROS to assess the efficacy and safety of alpelisib for the treatment of the heterogeneous manifestations of PROS.

Patient-level data will be abstracted from medical charts of all eligible patients at all participating sites and will be pooled and assessed. Trained personnel at each site will abstract medical chart data (see [Section 6.4](#) for additional information). Informed consent will be obtained prior to data abstraction, as appropriate, for eligible patients interested in participating in the study.

[figure not shown]
Patients with PROS who have received at least one dose of alpelisib initiated at least 24 weeks before the cut-off date will be included. The index (baseline) date will be defined as the date of alpelisib initiation. The pre-index date period will be defined as the period from up to 24 weeks prior to the index date through one day prior to the index date. The study period will be defined as the period from the index date up to the cut-off date ([Figure 6-1](#)).

The cut-off date (09-Mar-2020) is selected to minimize the impact of the COVID-19 pandemic on the data integrity. Eligible patients who initiated alpelisib on or before 23-Sep-2019 will have relevant assessments expected to occur on or before 09-Mar-2020. At that time of the cut-off, COVID-19 pandemic did not have major consequences on the regular management of the patients in the countries participating in the MAP.

Available information from all clinic visits during the pre-index date period will be abstracted; additionally, available prior PROS medications and PROS related surgical/vascular interventions will be collected since diagnosis.

During the study period, all available data will be collected from index date up to the cut-off date. If a patient has discontinued treatment prior to that date, only data reported up to 30 days after the last date of study treatment will be abstracted and entered into the database.

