### 6.2.1 Inclusion criteria

Patients will be included in this study if they meet all of the following inclusion criteria:

1. Patient (adult or pediatric) is $\geq 2$ years of age *
2. Patient has a physician confirmed/documented diagnosis of PROS*
3. Patient has a documented evidence of a mutation in the PIK3CA gene*
4. Patient's condition was assessed by the treating physician as severe or life threatening and treatment was deemed necessary*
5. Patient has been treated with at least one dose of alpelisib, initiated on or before 23-Sep-2019 (i.e. at least 24 weeks before the cut-off date of the 09-Mar-2020)
6. Patient has medical chart history available during enrollment in the MAP
7. Patient (in case of pediatric patients assent and/or parent/guardian consent) consented to participate in the study (as required by local ethics regulations)
* Inclusion criteria for MAP enrollment (assessed at the time of alpelisib initiation).

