1.3 Study design and settings

This study will be a site-based retrospective non-interventional medical chart review of pediatric and adult male and female patients with PROS.

Patients with PROS who have received at least one dose of alpelisib initiated at least 24 weeks before the cutoff date (09-Mar-2020) through a Novartis Managed access program (MAP) and satisfy the study inclusion criteria will be included in the study.

Patient-level data will be abstracted from medical charts of all eligible patients at all participating sites and will be pooled and assessed. Trained personnel at each site will abstract medical chart data. Informed consent will be obtained prior to data abstraction, as appropriate, for eligible patients interested in participating in the study where required.

[figure not shown]
The cut-off date of 09-Mar-2020 is selected to minimize the impact of the COVID-19 pandemic on the data integrity. Eligible patients who were initiated alpelisib on or before 23-Sep-2019 are expected to have 24 weeks of relevant assessments on or before 09-Mar-2020. At that time of the cut-off, COVID-19 pandemic did not have major consequences on the regular management of the patients in the countries participating in the MAP.

The **study period** will be defined as the period from the index date up to the cut-off date (09-Mar-2020) (Figure 1-1). During the study period all available data will be collected, if a patient has discontinued treatment prior to the cut-off date only data reported up to 30 days after the last date of study treatment will be abstracted and entered into the database.

The **index date (baseline)** will be defined as the date of alpelisib initiation. This date will be used as reference date for all assessments (safety and efficacy).

The **pre-index date** period will be defined as the period from up to 24 weeks prior to the index date (baseline) through to the day prior to the index date. (Figure 1-1).

Figure 1-1 Study design

Lesion assessments and definition

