An important aspect of treatment with alpelisib consist in the healthcare resources needed to care for patients with PROS. The necessity for frequent hospitalization and ER visits could have both an economic and a general health impact on PROS patients. The analyses below aims to describe the pattern observed in the study population.

The proportion of patients using non-medical resource, hospitals and ER visits will be reported, along with the relation to the disease, during the study period.

Moreover the same measure will be assessed as available for the pre-index period and reported separately, to assess the use of HRU and ER visits prior to start of alpelisib.

Table 3-7 Endpoints related to objective #8.

Measure	Type of variable	Summary Statistics	Timing
Proportion of patients using non-medical resource (e.g., physical therapy, occupational therapy, home school)	Binary	Frequency, percentage	Overall during study period
Proportion of patients using non-medical resource due to PROS (i.e., related or not related)	Binary	Frequency, percentage	Overall during study period
Frequency of non-medical resource use	Categorical	Frequency, percentage	Overall during study period
Proportion of patients with ≥ 1 hospitalization	Binary	Frequency, percentage	Overall during study period
Proportion of patients with ≥ 1 hospitalization related to PROS (i.e., related or not related)	Binary	Frequency, percentage	Overall during study period
Number of hospitalizations	Continuous	N, mean, median, standard deviation, Q1, Q3, minimum and maximum	Overall during study period
Number of hospitalizations related to PROS	Continuous	N, mean, median, standard deviation, Q1, Q3, minimum and maximum	Overall during study period
Duration of hospitalizations	Continuous	N, mean, median, standard deviation, Q1, Q3, minimum and maximum	Overall during study period
Duration of hospitalizations related to PROS	Continuous	N, mean, median, standard deviation, Q1, Q3, minimum and maximum	Overall during study period
Proportion of patients with ≥ 1 ER visit	Binary	Frequency, percentage	Overall during study period
Proportion of patients with ≥ 1 ER visit related to PROS (i.e., related or not related)	Binary	Frequency, percentage	Overall during study period
Number of ER visits	Continuous	N, mean, median, standard deviation, Q1, Q3, minimum and maximum	Overall during study period

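### For index dates from 1 January to about 17 June, SAP Table 4-1 dates a prior-year start known only by year before the pre-index window, even when the event began inside it

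*SAP*

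**What the plan says.** SAP 4.1 defines the pre-index period as running "from up to 24 weeks prior to the index date through to the day prior to the index date"; SAP 1.3 gives the same window. Protocol 6.1 ties pre-index abstraction to it: "Available information from all clinic visits during the pre-index date period will be abstracted". Only prior PROS medications and PROS-related surgical or vascular interventions are collected back to diagnosis.

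SAP 4.3.1, Table 4-1, imputes partial start dates for adverse events, symptoms and complications, medications and medical history, and also for "health resources utilization, non-drug treatment and other medical interventions". If day and month are missing, the rule is: "If available year < year of study treatment start date then 01JulYYYY". Table 4-3 covers laboratory tests, vital signs, surgery, questionnaires and similar items. Its rule for the same situation is bounded: "If available year < year of study treatment start date then max (01JulYYYY , Pre-Index date").

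SAP 4.3.1.1 assigns events to the pre-index or study period by end date, but only when the start is completely missing. It has no rule for a start known only by year. The last sentence of the main part of 4.3.1 promises similar imputation for the pre-index period and leaves the detail to the programming specifications.

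For health resource use, SAP 3.6 (objective 8) lists counts of hospitalizations and ER visits and the duration of hospitalization, then adds: "Moreover the same measure will be assessed as available for the pre-index period and reported separately". Protocol 6.8.2 explicitly includes mean pre-index duration of hospitalization.

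**The concern.** A fixed mid-year date is a reasonable default for medical history. It does not suit a short window that ends at the index date. If the window reaches into the prior year, it covers the later part of that year, and 1 July lies before all of it. A hospitalization, ER visit or closed symptom episode that began there and was recorded only by year is then always dated too early.

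What follows depends on a rule the SAP does not give. If periods are assigned by start date, the event leaves the pre-index summaries and the reference level falls. If they are assigned by end date or overlap, the event stays, but a hospital stay runs from 1 July and the reference duration rises. The study has no control group, so pre-index use is what on-treatment use will be read against under objective 8.

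The two sets of rules also sit badly together. With a wholly unknown start and an end before the index date, 4.3.1.1 places the event in the pre-index period. Once the chart also gives the year, that rule no longer applies and the event may be lost.

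**Working it through.** **Inputs.** Imputed start: 1 July of the recorded year (SAP Table 4-1). Window: index date minus 24 weeks to the day before index (SAP 4.1). Imputed ends: 31 December if only the year is known, end of the study period if completely missing (SAP Table 4-2). The SAP gives no formula for length of stay. I count both end days, as SAP 3.6 does for duration of first event; without the extra day, each length is one day shorter.

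**1. The plan's own date arithmetic.** Protocol 6.2.1 has alpelisib "initiated on or before 23-Sep-2019 (i.e. at least 24 weeks before the cut-off date of the 09-Mar-2020"). From 23-Sep-2019 to 09-Mar-2020 is 168 days = 24 × 7, so 24 weeks is 168 calendar days.

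**2. Can 1 July fall in the window?** The earliest index date in any year is 1 January, and 1 January − 168 days = 17 July of the prior year. From 1 July to 1 January is 184 days, and 184 − 168 = 16, so the imputed date is at least 16 days early. Every index date from 01-Jan-2014 to 23-Sep-2019 was checked (an assumed range, 2,092 dates). The prior-year 1 July lay inside the window for none.

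**3. Who is affected?** The window reaches into the prior year only if index − 168 days is 31 December or earlier, that is, for index dates from 1 January to 17 June (16 June in leap years). The share of the prior year inside the window is:

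| Index date (2019) | Window opens | Prior-year days in window | Share of prior year |
|---|---|---|---|
| 1 January | 17-Jul-2018 | 168 | 46% |
| 1 March | 14-Sep-2018 | 109 | 30% |
| 1 May | 14-Nov-2018 | 48 | 13% |
| 18 June | 01-Jan-2019 | 0 | 0% |

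**4. Length of stay if the event is kept.**
- Same-year discharge inside the window: from 1–17 July = 17 days to 1 July–31 December = 184 days. A year-only discharge gives 184.
- Discharge in the index year before the index date: 185 to 351 days. For example, 01-Jul-2018 to 10-Jan-2019 is 194.
- Discharge date missing: 01-Jul-2018 to 09-Mar-2020 is 618 days for a patient followed to the cut-off.

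**5. Illustration for the mean (assumed data).** Take 20 stays averaging 5 days, one of them recorded as 2018 to 20-Nov-2018. That stay becomes 143 days, and the mean is (19 × 5 + 143)/20 = 11.9. If it is cut at the window start for an index date of 01-Mar-2019, it runs from 14 September to 20 November = 68 days, and the mean is (95 + 68)/20 = 8.15. A bound alone therefore does not repair the duration summary.

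**6. Illustration for counts (assumed data).** With index dates spread evenly over the year, 168/365 = 46% of windows reach back, and about 23% of all pre-index days lie in the prior year. If 5% to 20% of records have year-only starts (an assumption) and periods are assigned by start date, the loss is 0.232 × 5% = 1.2% to 0.232 × 20% = 4.6% of pre-index events.

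**7. Would copying the Table 4-3 bound work?** I read its pre-index date as the start of the window. For an index date of 01-Mar-2019, a 2018 start becomes 14-Sep-2018, inside the window. But a 2016 start also becomes 14-Sep-2018. For an index date of 01-Sep-2019, a 2018 start becomes 17-Mar-2019, which contradicts the recorded year. The bound has to be conditional.

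**The case against.** The best defence is that 1 July is more often right than wrong. A visit note inside the window can mention an older admission, and nothing in the documents shows that the eCRF excludes it. If starts were spread evenly over the prior year, then averaged over the affected index dates only about 23% would fall in the window, and about 77% would truly precede it. Moving all of them in would inflate pre-index use and make use on alpelisib look improved.

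This stands as a warning against a blanket correction. It does not rescue the rule, because Protocol 6.1 aims pre-index abstraction at the window, so the records that reach the database should be weighted towards it. A reader might go further and infer that every such record lay in the window. The protocol makes that likely for many records but does not establish it.

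It is also fair to say that the programming specifications may settle the matter. They are not available here, however, and the SAP promises only similar imputation, which would repeat the gap.

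Finally, the analyses are descriptive, the endpoints are secondary, and Protocol 6.6 bases its precision table on 50 patients. That limits the importance of the point but does not remove it.

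**Conclusion.** The point holds in a narrow form. For index dates from 1 January to about 17 June, a year-only start in the year just before index is always dated before the window, including when the event began inside it. The SAP does not say what happens to the event next. The calendar result is exact. The size is unknown because neither document gives the number of year-only records. It is probably small, and the figures in steps 5 and 6 are illustrations only.

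A reader might infer more than the documents support:
- **That every prior-year start is displaced.** Starts two or more years before the index year, and prior-year starts with an index date from about 18 June, were already outside the window.
- **That 184 days is a ceiling, or applies to ER visits.** Later or missing ends give longer stays, and ER visits have no duration summary.
- **That pre-index data are the only comparator for objective 6.** SAP 3.6 reports symptoms and complications between the index date and the key time-points. Pre-index data are described separately.
- **That the direction of bias is known.** It depends on the missing assignment rule.

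**What to change.** 1. **Table 4-1, for health resource utilization and non-ongoing symptoms or complications only.** The new rule applies when three conditions hold: the recorded year is the year just before the index year; the window reaches into that year; and the record has a stop date in the window or was abstracted as a pre-index event. The start is then max(01JulYYYY, index date − 24 weeks), never later than the stop date. Keep 01JulYYYY in all other cases. Non-drug treatment can stay as it is, since SAP 3.6 summarizes it only over the study period.
2. **Section 4.3.1.1.** Assign events with a year-only start by end date, as is already done for completely missing starts. That rule needs an end date that is at least partly recorded. If there is none, the start from step 1 should decide; otherwise the end imputed by Table 4-2 would move the event into the study period.
3. **Length of stay.** Count hospital stays with a year-only admission, leave them out of the duration summary, and report how many were left out.

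The cost is SAP wording and a small programming change; no new data are needed. A few stays leave the duration summary. Some events that began before the window may be counted as pre-index, so report pre-index health resource counts with and without the imputed-start records.
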